9.3. Demographics and Other Baseline Characteristics

Demographics (e.g., age, sex, race, body weight, height, etc.) and other baseline characteristics will be summarized with descriptive statistics by treatment group for each analysis population.

9.4. Efficacy Analyses

9.4.1. Primary Efficacy Analysis

The primary efficacy endpoint is the change from baseline in ELF at Week 48. Missing change from baseline in ELF will be imputed using a multiple imputation (MI) method under the assumption of missing at random (MAR).

Sensitivity analysis under the assumption of missing not at random (e.g., pattern mixture model) will be performed. In addition, another sensitivity approach to impute the missing ELF measurement at Week 48 using the last observation carried forward (LOCF) method will be performed.

The primary efficacy endpoint will be analyzed using the Multiple Comparison Procedure – Modeling (MCP-Mod) approach to assess the dose-response relationship. Within the framework of the MCP-Mod procedure, the null hypothesis of no dose-response will be tested at the 5% significance level (two-sided) against the alternative hypothesis that there is a dose-response.

The primary efficacy analysis will be performed using the ITT population. The mITT, Full-Analysis and PP populations will be used as sensitivity analyses. Both MI approaches and LOCF approaches will be applied to the missing change from baseline ELF as sensitivity analysis for ITT, mITT, Full-Analysis, and PP populations.

9.4.2. Secondary Efficacy Analyses

The between-group comparisons (aldafermin doses vs placebo) of the change from baseline in ELF at Week 48 will be performed using an analysis of covariance (ANCOVA) model with effects for treatment, baseline T2D status (Yes/No) and the baseline outcome value as a covariate.

Between-group comparisons (aldafermin doses vs placebo) of the histologic response at Week 48 (by NASH CRN criteria) will be performed using the Cochran-Mantel-Haenszel (CMH) test stratified by baseline T2D status (Yes/No).

In addition, analyses will be performed for the following secondary efficacy endpoints:

- Changes from baseline in C4 and serum bile acids
- Changes from baseline in Pro-C3
- Changes from baseline in ALT, AST
- Changes from baseline in liver stiffness measure (LSM by FibroScan®)

All secondary efficacy endpoints will be analyzed using an analysis of covariance (ANCOVA) model with effects for treatment, baseline T2D status (Yes/No) and the baseline outcome value as a covariate.

All secondary efficacy endpoints will be performed using the ITT population. Full-Analysis, and PP populations will be used as sensitivity analyses.

No multiplicity adjustment will be made between the primary and secondary efficacy analyses to control the experiment-wise type I error rate, and thus all secondary efficacy analyses are exploratory in nature.

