Up to approximately 150 eligible subjects will be randomized into 1 of 4 treatment groups in a 3:2:2:3 ratio to receive either subcutaneous placebo, 0.3 mg aldafermin, 1 mg aldafermin, or 3 mg aldafermin, respectively. Under protocol Version 5.0 and subsequent versions, eligible subjects will no longer be randomized into the 0.3 mg aldafermin treatment group. Instead, subjects will be randomized into 1 of 3 treatment groups in a 4:3:4 ratio to receive either subcutaneous placebo, 1 mg aldafermin or 3 mg aldafermin, respectively. Subjects randomized to the 0.3 mg aldafermin treatment group prior to protocol Version 5.0 will continue to receive the same dose until treatment completion. No more than 30% of the remaining population will be enrolled with the expanded Baveno VI criteria.

Randomization will be stratified by clinical diagnosis of T2D versus no T2D to ensure planned allocation ratio of treatment groups within each stratum (see [Table 6](#) [Version 1.0-4.0], [Table 7](#) [Version 5.0], and [Figure 2](#)).

Table 6. Study Design 282-CC-207 (Versions 1.0-4.0)

[figure not shown]
| Treatment Group | Dose of aldafermin (mg) | Mode of Treatment | Regimen | Number of Subjects Planned |
|-------------------------------|-------------------------|-------------------|---------|----------------------------|
| 1 | 0 (Placebo) | | | 45 |
| 2 | 0.3 | | | 30 |
| 3 | 1 | Subcutaneous | Daily | 30 |
| 4 | 3 | | | 45 |
| Total Subjects Planned | | | | 150 |

Table 7. Study Design 282-CC-207 (Version 5.0)

| Treatment Group | Dose of aldafermin (mg) | Mode of Treatment | Regimen | Number of Subjects Planned |
|-------------------------------|-------------------------|-------------------|---------|----------------------------|
| 1 | 0 (Placebo) | | | 52 |
| 2 | 0.3 | | | 8 |
| 3 | 1 | Subcutaneous | Daily | 38 |
| 4 | 3 | | | 52 |
| Total Subjects Planned | | | | 150 |

Figure 2. Schematic Overview of the Study Design

ALPINE 4 Trial Design & Patient Population

Study drug self-administration instructions and training will be provided to the subjects and study drug kits will be dispensed. Subjects will self-administer in the clinic the first dose of aldafermin/ placebo (Day 1) and doses at Weeks 2, 6, 12, 18, 24, 30, 36, 42, and 48 study visits. Subjects will self-administer all other doses through Week 48 at home.

Self-administration should occur at a similar time for every dose in both the clinic and at home.

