9.2. Analysis Populations

Subjects will be analyzed using the following analysis populations:

- Intent to treat (ITT) population: all randomized subjects
- Modified ITT (mITT) population: all subjects who receive at least 2 weeks of study drug and have at least one valid, post-dose, on-treatment ELF score
- Safety population: all subjects who receive at least one dose (full or partial) of study drug
- Full-Analysis population: all randomized subjects who receive at least one dose (full or partial) of study drug and have at least one valid, non-missing post-dose efficacy/PD parameter value
- Per-Protocol (PP) population: a subset of subjects in the Full Analysis population who have valid, non-missing baseline and post-dose liver biopsy results and do not have protocol deviations that impact the liver biopsy assessments
- PK population: all randomized subjects who receive at least one dose (full or partial) of drug and have a qualified (i.e., above the lower limit of quantification) pre-dose and post-dose (at least one) PK assessment

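### Low priority, cheap improvement: the secondary models in section 9.4.2 have no randomisation-period term, although Table 7 implies that 40 of 52 placebo subjects (77%) enter after the 0.3 mg arm closed

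*Protocol*

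**What the plan says.** Section 4.1 starts with 3:2:2:3 allocation (placebo, 0.3, 1, 3 mg). From Version 5.0, "eligible subjects will no longer be randomized into the 0.3 mg aldafermin treatment group", and "subjects will be randomized into 1 of 3 treatment groups in a 4:3:4 ratio" (placebo, 1 mg, 3 mg). Table 7 plans 52, 8, 38 and 52 subjects. Section 5.1 also records that inclusion criterion 3 was deleted at Version 5.0.

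Section 9.4.2 provides for "between-group comparisons (aldafermin doses vs placebo) of the change from baseline in ELF at Week 48", using an ANCOVA "model with effects for treatment, baseline T2D status (Yes/No) and the baseline outcome value as a covariate". Comparisons of histologic response "will be performed using the Cochran-Mantel-Haenszel (CMH) test stratified by baseline T2D status (Yes/No"). On the population it states: "All secondary efficacy endpoints will be performed using the ITT population". Section 9.2 defines this as "Intent to treat (ITT) population: all randomized subjects". Nothing in the protocol leaves 0.3 mg out of the dose comparisons or limits its comparator to placebo subjects randomised at the same time. The same section adds that no multiplicity adjustment is made and "thus all secondary efficacy analyses are exploratory in nature".

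**The concern.** Before Version 5.0 a subject had a 20% chance of receiving 0.3 mg; afterwards the chance was zero. Randomisation therefore protects the 0.3 mg versus placebo contrast only within the first period. Under the stated models, the 0.3 mg subjects are compared with a placebo group drawn mostly from the second period, and neither model has a term for the difference.

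The boundary is more than a calendar date, because entry criteria changed at the same version. T2D and baseline value need not absorb such a change, and the CMH test does not adjust for baseline at all. What is at stake is the reported 0.3 mg estimate and its p-value. This point concerns only the ANCOVA and the CMH test; it makes no claim about the primary MCP-Mod analysis.

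**Working it through.** **1. Reproduce Table 7.** Inputs: 8 subjects at 0.3 mg, total 150, and the two ratios (section 4.1).

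- Before: 8 / (2/10) = 40 subjects, split 3:2:2:3 = 12/8/8/12.
- After: 150 − 40 = 110 subjects, split 4:3:4 over placebo, 1 mg and 3 mg = 40/30/40.
- Sum: 12+40 = 52; 8; 8+30 = 38; 12+40 = 52. All four rows of Table 7 agree.
- Placebo randomised after closure: 40/52 = 0.769. If 6 to 10 rather than 8 subjects entered 0.3 mg (total still 150), this share is 83% to 71%.

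**2. Bias per unit of between-period shift, no period term.** For each dose this is the dose arm's second-period share minus the placebo share.

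- 0.3 mg: 0 − 0.769 = −0.77.
- 1 mg: 30/38 − 40/52 = +0.02.
- 3 mg: 40/52 − 40/52 = 0.

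**3. Standard errors in SD units** (least squares on these counts, no other covariates).

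| Contrast with placebo | Without period | With period |
|---|---|---|
| 0.3 mg | √(1/8 + 1/52) = 0.380 | 0.410 (+8%) |
| 1 mg | 0.2134 | 0.2135 |
| 3 mg | 0.1961 | 0.1961 |

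Using only the 12 concurrent placebo subjects, the 0.3 mg figure would be √(1/8 + 1/12) = 0.456. The period-adjusted 0.410 is smaller because the additive term borrows the period difference from the 1 mg and 3 mg arms. Solving for the weights, 52% of the placebo weight falls on first-period and 48% on second-period subjects.

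**4. Size on the ELF scale.** The protocol gives no SD. A two-arm approximation to Table 11, SD = difference / [(1.96 + z_power) × √(2/(45 × 0.85))], gives 0.64–0.65 in five rows and 0.60 in the last. I take 0.65 as an assumption, with 0.5 and 0.8 as a range. The shifts are also assumed. RMSE = √(bias² + SE²), with SE = 0.65 × 0.380 = 0.247 without the term and 0.65 × 0.410 = 0.267 with it.

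| Assumed shift | Bias (×0.769) | RMSE without | RMSE with | Two-sided error without |
|---|---|---|---|---|
| 0 | 0 | 0.247 | 0.267 | 5% |
| 0.05 | 0.04 | 0.250 | 0.267 | 5.3% |
| 0.1 | 0.08 | 0.259 | 0.267 | 6.0% |
| 0.2 | 0.15 | 0.291 | 0.267 | 9.4% |

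The error rates come from simulating the stated ANCOVA (100,000 runs per cell, planned counts, no drop-out, no treatment effect; assumed baseline ELF SD 0.9, slope −0.2, 60% T2D). For the three non-zero shifts they are 5.4/6.8/12.0% at SD 0.5 and 5.1/5.6/7.7% at SD 0.8. If half the shift acts through baseline ELF, the SD 0.65 figures fall to 4.9/5.3/5.9%. With the period term the error is 4.9–5.0%.

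Break-even shift = SD × √(0.4100² − 0.3798²) / 0.769 = 0.10, 0.13 and 0.16 at SD 0.5, 0.65 and 0.8.

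**5. CMH information, n1 × n2 / N, summed over periods.**

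- 0.3 mg: 8×52/60 = 6.93 pooled; 8×12/20 = 4.80 stratified (−31%).
- 1 mg: 38×52/90 = 21.96; 8×12/20 + 30×40/70 = 21.94.
- 3 mg: 52×52/104 = 26; 12×12/24 + 40×40/80 = 26.

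An assumed 10-point shift in response gives a 7.7-point bias in the pooled 0.3 mg comparison. At assumed response rates of 30% versus 10%, exact power (T2D ignored) is 37% against all 52 placebo subjects and 21% against the 12 concurrent ones.

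**The case against.** The strongest objection is that the period term is not a clear gain. No drift is documented, and the break-even of about 0.13 ELF units exceeds the whole placebo change of 0.1 that section 9.1 assumes over 48 weeks. Below break-even the term makes total error worse. This stands, and it makes the benefit conditional.

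Second, an additive period term does not turn the ANCOVA into a concurrent comparison, since 48% of the placebo weight still comes from second-period subjects. It replaces an assumption of no shift with one of a common shift in the placebo, 1 mg and 3 mg arms. This also stands and should be stated in the plan.

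Third, nothing depends on the contrast: it is exploratory, with 8 subjects. That limits the priority. For the first histologic endpoint, which section 3.2 restricts to subjects with at least 1 point in each NAS category, even 8 versus 12 is a ceiling.

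Fourth, the SAP may deal with it. Section 9 lets the SAP override the protocol, but it expects no discrepancies, and section 9.4.2 does fix the model terms. This objection does not remove the point.

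A reader might infer that the 0.3 mg result is already biased, or that the 1 mg and 3 mg comparisons are compromised. The documents support neither: they show no drift, and the carry-over is only 0.02 for 1 mg and zero for 3 mg.

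**Conclusion.** The point holds as a low-priority improvement. The 77% follows from Table 7 and the two ratios. The carry-over of 0.77 follows from that share, on the plain reading that 0.3 mg is among the doses compared and that placebo is pooled across periods. The protocol's 24-week ELF changes for 0.3 mg and placebo (0.083 and 0.066, section 9.1) differ by only 0.017. An assumed shift of 0.05 would add a bias of 0.04, more than that difference but small against the standard error of 0.25. The realised size depends on an unknown shift, an assumed SD, and how much T2D and baseline ELF absorb. It would be wrong to read the term as a gain in precision: what it offers is protection of one exploratory contrast against a between-period shift.

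**What to change.** In section 9.4.2:

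- Add randomisation period (before versus from Version 5.0) to the ANCOVA and as a further CMH stratum.
- State that the additive ANCOVA term assumes the same period shift in the placebo, 1 mg and 3 mg arms.
- Report the 0.3 mg results descriptively. Label the histologic comparison as at most about 8 versus 12 concurrently randomised subjects, because the second-period stratum holds no 0.3 mg subjects and contributes nothing to it.

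The cost is a wording change and one model degree of freedom. At SD 0.65 the 0.3 mg RMSE is up to 0.020 higher if there is no shift. The 1 mg standard error changes by about 0.02% and the 3 mg one not at all. The 0.3 mg histologic test loses power it barely had, and splitting 8 versus 12 by T2D as well leaves very small cells, which is a further reason to keep it descriptive.

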9.4.3. Other Efficacy Analyses

The details of other efficacy analyses will be provided in the SAP.

9.4.4. Subgroup Analyses

9.5. Safety Analyses

Adverse events will be coded using the Medical Dictionary for Regulatory Activities (MedDRA). TEAEs will be summarized by primary system organ class and preferred term. Actual values and change from baseline values for vital signs, ECGs, clinical laboratory (hematology and chemistry) tests, and other continuous safety variables will be summarized with descriptive statistics. Concomitant medications, injection site reactions, and other categorical safety variables will be summarized with frequency and percentage distribution.

All safety analyses will be performed using the Safety population.

9.6. Interim Analysis

One interim analysis (IA) may be conducted for organizational decision making. The IA, if conducted, will include a review of selected safety and efficacy endpoints by treatment group. No formal hypothesis testing will be conducted. The study will not be stopped early based on the results. Results for individual subjects will not be shared with study site staff or subjects. Further details of the IAs will be included in the SAP.

9.7. Pharmacokinetics

[REDACTED]

[REDACTED]

[REDACTED]

[REDACTED]

10. SUPPORTING DOCUMENTATION AND OPERATIONAL CONSIDERATIONS

10.1. Regulatory, Ethical, and Study Oversight Considerations

This study will be conducted in accordance with the protocol and with the following:

- Ethical principles for medical subjects involving human subjects derived from the Declaration of Helsinki
- Applicable ICH Good Clinical Practice Guidelines
- Applicable laws and regulations

10.1.1. Informed Consent Process

This study will be conducted in compliance with International Conference on Harmonisation (ICH) E6 Good Clinical Practice: Consolidated Guidance pertaining to informed consent.

At the first visit, prior to initiation of any study-related procedures, subjects must give their written consent to participate in the study after having been informed about the nature and purpose of the study, participation/termination conditions, and risks and benefits.

The informed consent document must be signed and dated by the subject prior to study participation. A copy of the informed consent document must be provided to the subject. Signed consent forms must remain in the subject's study file and be available for verification by sponsor or its representative at any time.

10.1.2. Ethics Committee

This protocol, the informed consent document, and all relevant supporting data must be submitted to the IRB/EC for approval. IRB/EC approval of the protocol, informed consent document, and any advertisement used to recruit study subjects must be obtained before the study may be initiated.

The PI is responsible for keeping the IRB/EC advised of the progress of the study and of any changes made to the protocol as deemed appropriate, but in any case, at least once a year.

The PI is also responsible for notifying the IRB/EC of any reportable AEs that occur during the study.

10.1.3. Data Safety Monitoring Board (DSMB)

Please refer to [Section 8.5](#).

10.1.4. Protocol Adherence

The investigator must adhere to the protocol as detailed in this document and agree that the sponsor must approve any changes to the protocol prior to seeking approval from the institutional review board (IRB). There will be no alterations in the protocol without agreement between the sponsor and the investigator. There will be no alterations in the protocol affecting subject safety without the express written approval of the sponsor, investigator, and the IRB.

10.1.5. Confidentiality and Privacy

All information provided regarding the study, as well as all information collected/documenting during the course of the study, will be regarded as confidential. The investigator agrees not to disclose such information in any way without prior written permission from the sponsor.

Any publication of the results, either in part or in total (articles in journals or newspapers, oral presentations, abstracts, etc.) by the investigator or their representative(s), shall require prior notification and review, within a reasonable time frame, by the sponsor, and cannot be made in violation of the sponsor's confidentiality restrictions or to the detriment of the sponsor's intellectual property rights.

10.1.6. Clinical Monitoring

The sponsor or designee (e.g., Clinical Research Associate [CRA]) will be responsible for monitoring this clinical trial. The CRA will monitor the study conduct, proper CRF and source documentation completion and retention, and accurate study drug accountability. To this end, the CRA will visit the study site at suitable intervals and be in frequent contact through verbal and written communication. The investigator will grant access to all documents (related to the study and the individual participants) at any time these are requested. In turn, the CRA will adhere to all requirements for participant confidentiality as outlined in the informed consent form (ICF). The investigator and investigator's staff will be expected to cooperate with the CRA, to be available during a portion of the monitoring visit to answer questions, and to provide any missing information.

10.1.7. Quality Assurance and Quality Control

Each clinical site will perform internal quality management of study conduct, data and biological specimen collection, documentation, and completion. An individualized quality management plan may be developed to describe a site's quality management.

10.1.8. Records

The results from Screening and data collected during the study will be recorded in the subject's CRF. To maintain confidentiality, the subjects will be identified only by numbers and initials.

The completed CRFs will be transferred to the sponsor or designee. Copies of each CRF will be retained by the PI. All source documents, records, and reports will be retained by the clinic.

All primary source data or copies thereof (e.g., laboratory records, CRFs, data sheets, correspondence, photographs, and computer records) that are a result of the original observations and activities of the study and are necessary for the reconstruction and evaluation of any study report will be retained in the clinic archives.

The sponsor will inform the PI of the time period for retaining these records to comply with all applicable regulatory requirements. The minimum retention time will meet the strictest (longest) standard applicable to that site for the study, as dictated by any institutional

requirements or local laws or regulations, or sponsor standards/procedures; otherwise, the retention period will default to the retention period of 15 years following completion of the clinical trial.

Blood and tissue samples will be collected and any remaining or back-up study samples may be used for future exploratory and biomarker analysis related to aldafermin treatment or metabolic diseases. The samples will be stored for up to 15 years.

10.1.9. Financing and Insurance

The financing and insurance for this study are outlined in the Clinical Trial Agreement.

10.1.10. Publication Policy

NGM will retain ownership of all data. All proposed publications based on this study will be subject to sponsor's approval requirements.

11. REFERENCES

11.1. Clinical Studies Referenced in this Protocol

| Study No. | Phase | Study Title | Study Population |
|------------|-------|--|---|
| 12-0101 | 1 | A Phase 1 Randomized, Double Blind, Placebo Controlled, Single Ascending Dose and Multiple Ascending Dose Study to Evaluate the Safety, Tolerability, and Pharmacokinetics of NGM282 in Healthy Adult Participants | Normal volunteers |
| 282-RI-103 | 1 | A Phase 1, Single-center, Open label, Parallel group Study to Evaluate the Pharmacokinetics, Safety & Tolerability of a Single Dose of Aldafermin (NGM282) in Subjects with Impaired Renal Function | Renally impaired and normal volunteers |
| 13-0102 | 2a | A Randomized, Double Blind, Placebo Controlled, Parallel Group, Multiple Center Study to Evaluate the Safety, Tolerability, and Activity of NGM282 Administered for 28 Days to Participants with Type 2 Diabetes Mellitus | T2D |
| 13-0103 | 2a | A Phase 2, Randomized, Double Blind, Placebo Controlled, Parallel Group, Multiple Center Study to Evaluate the Safety, Tolerability, and Pharmacodynamic Activity of NGM282 in Combination with Ursodeoxycholic Acid (UDCA) Administered for 28 Days in Patients with Primary Biliary Cirrhosis (PBC) | PBC |
| 14-0104 | 2b | A Phase 2, Multicenter Study to Evaluate Four Doses of NGM282 Administered For 52 Weeks in Patients with Primary Biliary Cirrhosis (PBC) | PBC |
| 15-0105 | 2a | A Phase 2, Randomized, Double-Blind, Placebo Controlled, Parallel Group and An Open-Label Single-Blind Cohort Multiple Center Study to Evaluate the Safety, Tolerability, and Efficacy of NGM282 Administered for 12 Weeks in Patients with Histologically Confirmed Nonalcoholic Steatohepatitis (NASH) | NASH |
| 15-0106 | 2 | A Phase 2, Randomized, Double Blind, Placebo Controlled, Parallel Group, Multiple Center Study to Evaluate the Safety, Tolerability, and Efficacy of NGM282 Administered for 12 Weeks in Patients with Primary Sclerosing Cholangitis (PSC) | PSC |
| 15-0107 | 1b | A Phase 1b, Double-Blind, Placebo-controlled, Parallel-Group Multidose Study of the Pharmacodynamics of NGM282 on Colonic Transit, Bile acid Homeostasis, and Fecal Fat in Subjects with Functional Constipation Individuals | Functionally Constipated and Healthy Volunteers |

